12.2.2. SAEs after end of trial treatment

For 90 days after stop of afatinib, the following events have to be reported as SAE:

- fatal, life-threatening and other medically significant events possibly, probably or definitely related to late effects of trial treatment
- disabling events
- second primary cancer
- congenital anomaly

In the case of pregnancy occurring during trial treatment or within 1 year after treatment discontinuation, the investigator shall immediately notify this by completing the pregnancy reporting form. The investigator shall ensure that the case is followed up to the end of the pregnancy and supply a final report on the outcome.

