9.2. Adverse Events of Special Interest

Drug-induced liver injury (DILI):

- For patients with normal liver function at baseline:
Hepatic injury defined by an elevation of AST and/or ALT >3 × ULN combined with an elevation of bilirubin $>2 \times \text{ULN}$ measured in the same blood draw sample.
- For patients with impaired function tests at baseline:
Hepatic injury defined by an elevation of AST and/or ALT >5 × ULN combined with an elevation of bilirubin $>2 \times \text{ULN}$ measured in the same blood draw sample.

Adverse Events of Special Interest are to be reported in an expedited manner like Serious Adverse Events, even if they do not meet any of the seriousness criteria. Please submit the completed SAE Initial Report Tab in the RDE system within 24 hours after awareness of the event, and choose “yes” in the “description” section if this is a “non-serious adverse event of special interest”. Please submit the SAE Follow-up Report within 14 days after the Initial Report.

10. Trial treatment

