12.2. Definition of Serious Adverse Event (SAE)

12.2.1. SAEs during trial treatment

An SAE is defined in general as any undesirable medical occurrence/adverse drug experience that occurs during or within 90 days after stopping trial treatment that results in any of the following:

- is fatal (any cause except progression of disease)
- life-threatening,
- requires or prolongs inpatient hospitalisation,
- results in persistent or significant disability/incapacity
- is a congenital anomaly or birth defect
- is a secondary malignancy
- is a medically important event
- Overdose, only if associated with a symptom or AE

Second (non-NSCLC) malignancies are always considered SAEs, no matter when they are diagnosed. These events should be reported on the Serious Adverse Event Forms.

Other significant/important medical events which may jeopardise the patient are also considered serious adverse events.

An overdose is defined as the accidental or intentional administration of any dose of a product that is considered both excessive and medically important. All occurrences of overdose must be reported as an SAE.

Serious also includes any other event that the investigator or the ETOP Safety Office judges to be serious or which is defined as serious by the regulatory agency in the country in which the event occurred.

An unexpected adverse event is one that is not listed as a known toxicity of the investigational drug in the summary of product characteristics.

A related adverse event is one for which the investigator assesses that there is a reasonable possibility that the event is related to the investigational drug. All adverse events judged as having a reasonable suspected causal relationship to the trial medication qualify as adverse reactions.

Events not considered to be serious adverse events are hospitalisations occurring under the following circumstances:

- elective surgery;
- occur on an outpatient basis and do not result in admission (hospitalisation < 24 h);
- are part of the normal treatment or monitoring of the studied treatment;
- progression of disease (by convention, clinical events related to the primary cancer being studied or to the primary cancer progression are not to be reported as SAEs,

even if they meet any of the seriousness criteria from the standard SAE definition, **unless** the event is more severe than expected and therefore the investigator considers that their clinical significance deserves reporting).

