12.5. Reporting SAEs and Adverse Events of Special Interest

Drug-induced liver injuries as defined in section 9.2 are considered to be Adverse Events of Special Interest (AESIs) and are to be reported on the SAE form, within 24 hours of awareness.

Following the subject's written consent to participate in the trial, all SAEs, whether related or not related to trial drug, must be collected, including those thought to be associated with protocol-specified procedures. All SAEs must be collected that occur within 90 days of discontinuation of dosing.

All SAEs must be collected that occur during the screening period. If applicable, SAEs must be collected that relate to any protocol-specified procedure (eg, a follow-up skin biopsy). The investigator should report any SAE that occurs after these time periods that is suspected to be related to trial drug or protocol-specified procedure.

Any SAE or AESI must be reported by submitting the completed SAE Initial Report Tab in the RDE system within 24 hours of awareness.

Submission is done via the remote data entry system, or in case of unavailability, by sending the SAE form by fax to the ETOP Safety Office:

[contact]

Once the remote data entry system is available again, the SAE Tab has to be completed by the site.

The SAE/AESI outcome must be reported within 14 days after onset by online submitting the SAE/AESI Follow-up Report Tab. In case the SAE is reported as ongoing after 14 days, the follow-up report has to be submitted again with the final outcome.

The ETOP Safety Office will forward each SAE to the trial chairs and notify principal investigators of any SAR meeting the criteria for expedited reporting (SUSAR) within the timelines specified in GCP.

The local Ethics Committee must be informed by the principal investigator about SAEs according to local regulations.

The ETOP Safety Office will inform Boehringer Ingelheim Regional Drug Safety and other appropriate persons about all SAEs and AESIs at least possibly related to trial medication (per either investigator or ETOP Safety Office review) within 24 hours of receipt.

The ETOP Safety Office will record the SAE and prepare an annual safety report (DSUR, Development Safety Update Report). Listings of SAEs will be prepared as required.

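### Protocol section 12.2.2 sets a narrower SAE scope for the 90 days after afatinib than sections 12.2.1 and 12.5, and 12.2.1 gives two overdose rules

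*Protocol*

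**What the plan says.** **Post-treatment scope.** Section 12.2.1 is headed as the on-treatment section, but its definition covers any qualifying event that "occurs during or within 90 days after stopping trial treatment that results in any of the following". The criteria that follow include inpatient hospitalisation and death from any cause other than progression, with no condition on relatedness. Section 12.5 agrees: SAEs are collected whether or not they are related to the drug, and "All SAEs must be collected that occur within 90 days of discontinuation of dosing".

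Section 12.2.2 is the one headed for the period after treatment. For those same 90 days it names what must be reported: "fatal, life-threatening and other medically significant events possibly, probably or definitely related to late effects of trial treatment", then disabling events, second primary cancers and congenital anomalies.

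**Overdose.** One item in the 12.2.1 list reads "Overdose, only if associated with a symptom or AE". Later in the same section: "All occurrences of overdose must be reported as an SAE". Just before that second sentence, overdose is defined as a dose judged both excessive and medically important.

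**AE capture.** Section 12.1 collects every AE up to 90 days after the last dose regardless of relatedness, with grade and relationship recorded.

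**SAP.** Section 5 and Tables 18 to 25 tabulate AEs and SAEs. The SAP gives no SAE definition or window of its own.

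**The concern.** A site that wants the rule for a patient who has stopped afatinib will naturally open 12.2.2, because its heading matches the question. That section makes the report depend on the investigator's own causality judgement for most event types and does not name hospitalisation. Neither document says which section prevails.

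Safety and tolerability is a stated secondary objective, and three things are at stake. An event recorded only as an AE does not trigger the 24-hour report. It also does not reach the safety office as an SAE. Section 12.5 relies on causality as judged by either the investigator or the safety office, so a site that filters on its own judgement removes the second opinion. Finally, the event gets no SAE narrative.

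The window is not marginal. Treatment stops at documented progression (section 11.9), and SAP section 1.2 reports that 6 of 13 patients had not reached week 12 free of progression. Twelve weeks is 12 × 7 = 84 days, so for such patients the 90 days after stopping may be as long as, or longer than, the time on drug.

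**Working it through.** The plan states no figure to reproduce, so the check compares the texts and adds two small sums.

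**1. Scope.** Take an event on day 30 after the last dose that is neither progression nor management of the underlying cancer, and is not one of the hospitalisations 12.2.1 excludes (such as elective surgery or stays under 24 hours).

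| Event | SAE under 12.2.1 and 12.5 | On the 12.2.2 list | AE under 12.1 |
|---|---|---|---|
| Unrelated death | Yes | No | Yes |
| Unrelated life-threatening event | Yes | No | Yes |
| Unrelated hospitalisation | Yes | No | Yes |
| Related hospitalisation | Yes | Not by name; only if judged medically significant | Yes |
| Disabling event, unrelated | Yes | Yes | Yes |
| Second cancer | Yes | Yes | Yes |

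The sections part on the first three rows and possibly on the fourth. In every row the AE record should still exist.

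**2. Overdose.** Take a dose judged excessive and medically important, with no symptom. The list item in 12.2.1 says it is not an SAE; the later sentence says it is. If there is a symptom, both say it is. If the dose is not judged medically important, the stated definition of overdose is not met. The conflict is therefore confined to asymptomatic overdoses that meet the definition.

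**3. SAP outputs.** The exposed outputs are those that count or describe SAEs as such: the SAE row of Table 18, Table 20 (patients by number of SAEs) and Table 25 (narratives). Tables 21 and 22 show AEs and SAEs by grade; if the two are pooled there, reclassifying an event changes little. Table 24 lists AEs by patient, and SAP section 5 says that listing carries grade, dates, relation and outcome.

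If all 13 enrolled patients are in the safety cohort (an assumption), one patient whose only SAE is left unflagged moves the Table 18 SAE percentage by 1/13 = 7.7 points. A patient who already has another SAE does not move it.

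**4. Minor mismatches.**
- Second malignancy. Section 12.2.1 says: "Second (non-NSCLC) malignancies are always considered SAEs, no matter when they are diagnosed". Section 12.2.2 lists second cancers under its 90 days, and 12.5 asks for later SAEs only when they are suspected to be related to the drug or a procedure.
- Follow-up report. Section 12.5 says: "The SAE/AESI outcome must be reported within 14 days after onset". Section 9.2, on AEs of special interest, says: "Please submit the SAE Follow-up Report within 14 days after the Initial Report", and Table 12 agrees with 9.2. The initial report is due 24 hours after awareness. With an awareness lag of L days (an assumption), the first rule falls due on day 14 from onset and the second by day L + 1 + 14. For L = 0 that is day 14 against day 15. For L = 21, one three-week visit interval, it is day 14 against day 36. Once L exceeds 14 the 12.5 date has passed before the site knows of the event.

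**The case against.** The strongest defence is that 12.2.2 does not say only. It could be meant to stress the late effects that matter most, with 12.5 as the operative collection rule. That is possible, but the text does not say so. A list that adds a relatedness condition to events already reportable without one has no purpose if it is not a limit.

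The second defence is stronger. A reader might infer that unrelated post-treatment events drop out of the trial data and cannot be examined later. The documents do not support that. Sections 12.1, 15.7 and 15.8 and Table 12 keep AE collection open for 90 days, and 12.1 records relatedness. What is lost is the SAE flag, the expedited report, the safety office's review and the narrative.

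A reader might also infer that every mismatch in these sections decides which events reach the safety office. The 14-day clock does not: the initial report has already been made, so it only sets when the outcome is due. The second-malignancy passages can largely be read together, since 12.2.2 does not exempt later cancers. One gap remains there: a second cancer found after 90 days is outside the general AE window, so a site relying on 12.2.2 or 12.5 could leave it unreported.

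Finally, a reader might want to know how many patients are affected. The documents give no SAE rate, exclude most progression-related events, and keep disabling events and second cancers reportable under 12.2.2 without a relatedness filter. Any count would rest wholly on an assumed rate, so none is given.

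**Conclusion.** The contradiction is real and stands in the current protocol. For the 90 days after stopping, 12.2.2 is narrower than 12.2.1 and 12.5 on unrelated deaths not due to progression, unrelated life-threatening events and unrelated hospitalisations. The two overdose sentences in 12.2.1 cannot both be followed for an asymptomatic overdose that meets the stated definition.

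The effect is on classification and expedited handling. It falls mainly on the SAE row of SAP Table 18 and on Tables 20 and 25, while total AE counts should change little. The conclusion rests on two assumptions: that at least some sites work from 12.2.2, and that AE collection under 12.1 is carried out as written. The primary endpoint, the two-stage design and the decision rule are unaffected. It should be corrected, but it does not threaten the trial's main result.

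**What to change.** 1. **Protocol scope.** Reconcile the passages by replacing the 12.2.2 list with a reference to the scope in 12.5, which 12.2.1 already matches for this window. The pregnancy paragraph after the list is a separate matter and stays.
2. **Overdose.** Keep one sentence in 12.2.1, consistent with the definition given there.
3. **SAP.** State the SAE definition and window behind Tables 18, 20 and 25.
4. **Data check.** SAP section 1.2 reports that accrual is permanently closed, so rewording cannot restore flags for windows already past. Before database lock, compare post-treatment AEs with the stated definition and query sites where an SAE form seems to be missing. Grade 4 and 5 events can be found from the recorded grade. Hospitalisation is not among the items SAP section 5 lists for the by-patient AE table, so it may need a direct query.
5. **Minor alignments.** Make the second-malignancy window explicit and identical in 12.2.1, 12.2.2 and 12.5. Use one start point for the 14-day follow-up report in 9.2, 12.5 and Table 12.

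The cost is a wording change in the protocol, a sentence or two in the SAP, a few more SAE forms and some query work.

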12.3. Definition of Serious Adverse Reaction (SAR)

SARs are all SAEs considered to be related (possibly, probably, definitely) to the trial treatment.

12.4. Definition of Suspected Unexpected Serious Adverse Reaction (SUSAR)

A SUSAR is a serious adverse reaction that is assessed as unexpected on the basis of the applicable Swiss product information, the European summary of product characteristics, and the Investigators' Brochure.

12.5. Reporting SAEs and Adverse Events of Special Interest

Drug-induced liver injuries as defined in section 9.2 are considered to be Adverse Events of Special Interest (AESIs) and are to be reported on the SAE form, within 24 hours of awareness.

Following the subject's written consent to participate in the trial, all SAEs, whether related or not related to trial drug, must be collected, including those thought to be associated with protocol-specified procedures. All SAEs must be collected that occur within 90 days of discontinuation of dosing.

All SAEs must be collected that occur during the screening period. If applicable, SAEs must be collected that relate to any protocol-specified procedure (eg, a follow-up skin biopsy). The investigator should report any SAE that occurs after these time periods that is suspected to be related to trial drug or protocol-specified procedure.

Any SAE or AESI must be reported by submitting the completed SAE Initial Report Tab in the RDE system within 24 hours of awareness.

Submission is done via the remote data entry system, or in case of unavailability, by sending the SAE form by fax to the ETOP Safety Office:

[contact]

Once the remote data entry system is available again, the SAE Tab has to be completed by the site.

The SAE/AESI outcome must be reported within 14 days after onset by online submitting the SAE/AESI Follow-up Report Tab. In case the SAE is reported as ongoing after 14 days, the follow-up report has to be submitted again with the final outcome.

The ETOP Safety Office will forward each SAE to the trial chairs and notify principal investigators of any SAR meeting the criteria for expedited reporting (SUSAR) within the timelines specified in GCP.

The local Ethics Committee must be informed by the principal investigator about SAEs according to local regulations.

The ETOP Safety Office will inform Boehringer Ingelheim Regional Drug Safety and other appropriate persons about all SAEs and AESIs at least possibly related to trial medication (per either investigator or ETOP Safety Office review) within 24 hours of receipt.

The ETOP Safety Office will record the SAE and prepare an annual safety report (DSUR, Development Safety Update Report). Listings of SAEs will be prepared as required.

12.6. Pregnancy

If, following initiation of the investigational product, it is subsequently discovered that a patient is pregnant or may have been pregnant at the time of investigational product exposure, the investigational product will be permanently discontinued in an appropriate manner (eg, dose tapering if necessary for subject safety).

The investigator must inform ETOP within 24h of awareness by completing and submitting the Pregnancy Form in ETOPdata.

Follow-up information regarding the course of the pregnancy, including perinatal and neonatal outcome and, where applicable, offspring information must be reported on the Pregnancy Form.

In case the pregnancy is associated with a serious adverse event (fetal death, congenital anomaly, abortion, complication requiring hospitalisation), this has to be reported on the SAE form within 24h.

Any pregnancy that occurs in a female partner of a male trial participant should be reported to ETOP. Information on this pregnancy will be collected on the Pregnancy Form.

13. Response evaluation

13.1. RECIST 1.1 criteria

The patient's response to protocol treatment will be assessed by RECIST 1.1 criteria (see appendix 2).

13.2. Determination of time point response

Table 11. Determination of time point response

Target lesions	Non-target lesions	New lesions	Resulting Overall response
CR	CR	No	CR
CR	Non-CR / non-PD	No	PR
CR	Not evaluated	No	PR
PR	Non-PD or not all evaluated	No	PR
SD	Non-PD or not all evaluated	No	SD
Not all evaluated	Non-PD	No	NE unless the sum of diameters of evaluated lesions indicates PD ¹⁾
PD	Any	Yes or no	PD
Any	PD	Yes or no	PD
Any	Any	Yes	PD

- 1) From ref. 1 in Appendix 2, p.234: When no imaging/measurement is done at all at a particular time point, the patient is not evaluable (NE) at that time point. If only a subset of lesion measurements are made at an assessment, usually the case is also considered NE at that time point, unless a convincing argument can be made that the contribution of the individual missing lesion(s) would not change the assigned time point response. This would be most likely to happen in the case of PD. For example, if a patient had a baseline sum of 50mm with three measured lesions and at follow-up only two lesions were assessed, but those gave a sum of 80 mm, the patient will have achieved PD status, regardless of the contribution of the missing lesion.

13.3. Determination of best overall response

Best overall response is defined as best response across all time points. Confirmation of partial or complete response by an additional scan is not requested in this trial. Response at week 6 assessment will be confirmed by the week 12 assessment; response at week 12 assessment will be confirmed by the week 20 assessment.

14. Endpoints definition

14.1. Disease control

This is the primary endpoint. It is defined as complete or partial response, or disease stabilisation lasting at least 12 weeks.

14.2. Progression-free survival

This is defined as the time from the date of enrolment until documented progression or death, if progression is not documented. Censoring will occur at the last tumour assessment only if patient is lost to follow-up.

14.3. Objective response

Objective response is defined as best overall response (CR or PR) across all assessment time-points during the period from enrolment to termination of trial treatment. Objective response to afatinib treatment will be determined using RECIST 1.1 criteria (see section 13).

14.4. Overall survival

Defined as time from the date of enrolment until death from any cause. Censoring will occur at the last follow-up date.

14.5. Toxicity

Adverse events classified according to NCI CTCAE version 4.

15. Trial procedures

This section gives an overview of procedures, clinical and laboratory evaluations and follow-up investigations.

15.1. Baseline evaluations (within 28 days prior to enrolment)

The following examinations should be done within a maximum of 28 days before enrolment. If examinations were done prior to 28 days before enrolment, they have to be repeated.

- 15.1.1. Obtain written informed consent prior to any trial-specific evaluations or interventions
- 15.1.2. Local *HER2* mutation testing (test may have been done prior to 28 days)
- 15.1.3. Medical history including symptoms, smoking history, medications, comorbidities and allergies
- 15.1.4. Physical examination according to local standards, including blood pressure [mmHg], ECOG performance status, body weight [kg]
- 15.1.5. Haematology: WBC, haemoglobin, platelets, neutrophils. Needs to be repeated

prior to first dose of afatinib if done more than 7 days prior to first dose.

- 15.1.6. Chemistry: sodium (Na), potassium (K), calcium, albumin, magnesium. Needs to be repeated prior to first dose of afatinib if done more than 7 days prior to first dose.
- 15.1.7. Renal function: serum creatinine and creatinine clearance calculated according to Cockcroft-Gault
- 15.1.8. Hepatic function: ALT, AST, bilirubin, GGT
- 15.1.9. Electrocardiogram
- 15.1.10. Pregnancy test for women of childbearing potential within 7 days before trial treatment start
- 15.1.11. CT thorax and upper abdomen. PET-CT thorax and upper abdomen can be used instead of CT scan if contrast-enhanced
- 15.1.12. Brain MRI or CT
- 15.1.13. Ascertain availability of FFPE tumour material for later central review of *HER2* mutation

15.2. At trial treatment start visit

Week 0 is the week of trial treatment start. The following evaluations should be done at the week 0 visit:

- 15.2.1. If not done within 7 days prior to first dose, repeat haematology and chemistry *before* first dose: WBC, haemoglobin, platelets, neutrophils; sodium, potassium, calcium, albumin, magnesium (to be reported on baseline form)
- 15.2.2. Record current symptoms, and all adverse events which have occurred after signing informed consent, on adverse event CRF
- 15.2.3. Record all concomitant medication from date of signed informed consent.

